**Not applicable**

**Number of Subjects:** What is the anticipated number of subjects to be enrolled at UVM/UVM Medical Center and in the case of a multi-center study, with UVM/UVM Medical Center as the lead, the total number of subjects for the entire study.

**Participants:** In order to complete testing on 48 **non-smoking** healthy older adults, aged 65-75 years and 48 **non-smoking** healthy younger adults, aged 21-30 years, we will screen 58 potential participants in each age group for a total of 116. An equal number of men and women will be recruited. During the drug challenge phase of the study younger female participants will be tested in the follicular phase of their menstrual cycles and will have a negative pregnancy test before each session. The older adult group will be carefully screened using a neuropsychological assessment (below) to ensure they do not have MCI or pre-MCI. In both age groups, we anticipate a dropout rate of approximately 20%, as has been our experience in our prior studies. We aim to have 48 older and 48 younger participants complete the study for a total of 96 participants.

**Inclusion/Exclusion Criteria:** Eligibility and ineligibility criteria should be specific. Describe how eligibility will be determined and by whom. Changes to the eligibility criteria at a later phase of the research have the potential to invalidate the research.

**Cognitive/Behavioral Screening:** All **older participants** will be cognitively and behaviorally assessed using standard tests designed to exclude participants with significant cognitive or behavioral impairment including the Mini Mental State Exam (MMSE) (Folstein et al. 1975), Brief Cognitive Rating Scale (Reisberg et al. 1993b), the Mattis Dementia Rating Scale (Jurica et al. 2001), and the Global Deterioration Scale (GDS) (Reisberg et al. 1993a). Participants will be required to have a GDS score of 1-2, a MMSE score of greater than or equal to 27, and score above 130 on the Mattis scale. Older participants will have an informant complete the Informant Questionnaire on Cognitive Decline in the Elderly (IQCODE; Jorm 2004) and have scores of 3 or less indicating no cognitive change.

All **older and younger participants** will undergo the following behavioral screening measures: a Structured Clinical Interview for DSM-IV-TR (SCID) (First et al. 2001) to establish the presence/absence of Axis I psychiatric disorders, and the Beck Depression Rating Scale (BDI, score < 10) (Beck et al. 1961). Participants will be excluded if they have a current Axis 1 disorder. All participants will perform the Wechsler Abbreviated Scale of Intelligence (WASI) to assess IQ and will be required to score above 80.

**Neuropsychological Screening:** In an effort to ensure the older adults are not at the beginning stages of MCI or dementia and to assess general neuropsychological functioning, **older and younger participants** will be screened with the **Repeatable Battery for the Assessment of Neuropsychological Status (RBANS)** (Randolph 1998). RBANS was developed for the dual purposes of identifying and characterizing abnormal cognitive decline in older adults and as a neuropsychological screening battery for younger adults. The RBANS assesses five cognitive domains including immediate memory, language, visuospatial/constructional ability, attention, and delayed memory and provides a global total measure. Each participant will need to score within one standard deviation (SD) of the mean for her/his age. A measure of executive functioning is missing from the RBANS so we will include selected measures from the **Delis-Kaplan Executive Function System (D-KEFS)**. Specifically we will include the Trail Making Test and Verbal Fluency subtests. All participants will be required to score within one SD of the mean for their age.

**Medical Screening:** Participants will be physically healthy **nonsmokers** with a BMI  $\leq 32 \text{ kg/m}^2$ , and no cardiovascular disease other than mild hypertension. Participants will be assessed by history, physical exam, and laboratory tests assessing cardiac, hematopoietic, renal, hepatic, and hormonal function (CBC, CMP, TSH, U/A, ECG), and will have a medical history review and physical examination to establish general physical health. Blood will also be obtained for an **exploratory genetic analysis** to examine APOE and COMT genotypes as these genes have been shown to be important in cognition in older adults. APOE is important for cognitive decline in older adults and associated with cholinergic function (Espeseth et al, 2006). The COMT ValMet polymorphism modulates working memory performance in psychiatric populations (e.g. Meyer-Lindenberg & Weinberger 2006) but not in healthy subjects (Blanchard et al. 2011). However, it affects working memory-related brain activation (Jacobs & D'Esposito 2011). Depending on the distribution of genotypes we will use this information as a covariate in the imaging analysis described below.

**Inclusion of Minorities and Women:** Describe efforts to include minorities and women. If either minorities or women are excluded, include a justification for the exclusion.

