## METHODS AND PROCEDURES

**Study Design:** Describe the research design, including a description of any new methodology and its advantage over existing methodologies.

**Design:** Older adults (aged 65-75 years) and younger adults (aged 21-30 years) will participate in a screening visit and then three (3) nicotinic challenge study days which include performing a working memory task during fMRI. The nicotinic challenges will consist of 1) 20 mg oral mecamylamine, 2) 7 mg transdermal nicotine, and 3) matching placebos. After an extensive medical, behavioral, and cognitive screening we will enroll and complete 48 older adults and 48 younger adults.

**Procedures:** Describe all procedures (sequentially) to which human participants will be subjected. Identify all procedures that are considered experimental and/or procedures performed exclusively for research purposes. Describe the types, frequency and duration of tests, study visits, interviews, questionnaires, etc. Include required screening procedures performed before enrollment and while on study. Please provide in table, list or outline format for ease of review. (describe and attach all instruments)

Note: A clinical research protocol may involve interventions that are strictly experimental or it may involve some aspect of research (e.g., randomization among standard treatments for collection and analysis of routine clinical data for research purposes). It is important for this section to distinguish between interventions that are experimental and/or carried out for research purposes versus those procedures that are considered standard therapy. In addition, routine procedures performed solely for research purposes (e.g., additional diagnostic/follow-up tests) should be identified.

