**Sample Size Calculations:** The sample size calculations are based on pilot data collected in our laboratory in separate studies: 1) older women with MECA and placebo challenges 2) younger adults during NIC and placebo challenges, and 3) older and younger adults with no challenge. We assume that, while the **fMRI** changes in younger adults will be in the same direction as older adults, the magnitude of the changes will be smaller. fMRI performed in younger adults during a 3-back condition showed a mean beta value of -1.12 in the **MFG**, compared to a mean of -0.54 in older adults. We assume that the MECA challenge in the younger adults will increase activation to a mean beta value mimicking that of the older adults on placebo (-0.54), while older adults will have an even greater activation increase to a mean beta of 1.00. Assuming a standard deviation of 0.40, a correlation of 0.35, both calculated from our pilot data, and a Type I error rate of 0.001, 13 subjects will provide 90% power to detect differences between younger and older adults in this region after MECA compared to placebo. A sample size of 19 younger adults and seven older adults will provide greater than 90% power to detect the within-group differences as statistically significant.

For **working memory performance**, sample size calculations are based on a Type I error rate of 0.05. The mean proportion correct for the 3-back performance in older adults was 0.75 compared to a mean of 0.88 in the younger adults, with a standard deviation of 0.13. We predict that the effect of the **MECA** challenge will be to reduce this accuracy measure in both the younger and older adults, with the older adults proportion correct decreasing to 0.60 while the decrease in younger adults will be less severe, decreasing to 0.83. Assuming a correlation of 0.35 a total of **48 subjects** will provide 90% power to detect differences on this test with MECA compared to placebo. This sample size will be sufficient to provide 90% power to detect a statistically significant decrease in performance among the older adults.

Consistent with our results of younger adults following **NIC** challenge, we assume that the effects of this stimulation will be in the opposite direction but similar in magnitude to those outlined above. We assume approximately a 20% drop-out rate; therefore, we will recruit 56 subjects/group, with the goal of **48 subjects/age group** completing the study.

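### At the plan's own 20% dropout, neither accrual figure (58 screened or 56 recruited per age group) yields 48 completers, and no allowance for screen failure is stated

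*Combined protocol and SAP*

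**What the plan says.** The Subject Selection and Number of Subjects sections carry the same paragraph. To complete testing on 48 people in each age group, "we will screen 58 potential participants in each age group for a total of 116". It goes on: "In both age groups, we anticipate a dropout rate of approximately 20%, as has been our experience in our prior studies". The target is then repeated: "We aim to have 48 older and 48 younger participants complete the study for a total of 96 participants".

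Sample Size Calculations gives a different accrual figure. It says "We assume approximately a 20% drop-out rate" and continues "therefore, we will recruit 56 subjects/group", again aiming at 48 completers per age group.

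Study Design places eligibility before enrolment: "After an extensive medical, behavioral, and cognitive screening we will enroll and complete 48 older adults and 48 younger adults". The Medical Screening text agrees, since challenge days are booked only for people who have passed.

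The Inclusion/Exclusion Criteria set out what has to be passed. On the RBANS, "Each participant will need to score within one standard deviation (SD) of the mean for her/his age", and a one-SD rule also applies to the D-KEFS measures. Both groups must also meet psychiatric, depression-score, IQ, BMI, smoking and cardiovascular criteria. Older adults must in addition meet GDS, MMSE, Mattis and IQCODE limits. No expected screen-failure rate appears anywhere.

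**The concern.** Three counts are needed to plan accrual: how many are screened, how many of those are enrolled, and how many of those complete. The plan gives 58, 56 and 48 under two of these labels plus the completer target, in different sections, without linking them. Each of 58 and 56 is tied separately to 48 completers and to the same dropout rate, so each can be checked against that rate.

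The form's question under Number of Subjects asks how many are expected to be enrolled, so 116 is the accrual figure that the IRB sees. The 48 per group is what supports the stated 90% power for the working-memory comparison. If the accrual figure does not lead to 48, either the trial finishes with less power than stated or accrual has to be raised partway through.

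**Working it through.** **Inputs from the documents.** Screened 58 per group, recruited 56, completers 48, dropout about 20%. For power: 3-back accuracy in older adults 0.75 falling to 0.60 on mecamylamine, in younger adults 0.88 falling to 0.83, SD 0.13, correlation 0.35, Type I error 0.05 (two-sided assumed).

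**1. Reproducing the 58.** 48 x (1 + 0.20) = 57.6, rounded up to 58. The form that allows for 20% loss is 48 / (1 - 0.20) = 60.

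**2. The 56 does not follow from 20%.** 1 - 48/56 = 0.143, so 56 implies 14.3% dropout.

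**3. Completers with no screen failures.**
- 58 x 0.80 = 46.4. With independent dropout at 20%, the chance of at least 48 completers out of 58 is 37%.
- 56 x 0.80 = 44.8.

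**4. Reproducing the 48 as a per-group number.** The SD of the within-person change is 0.13 x sqrt(2 x (1 - 0.35)) = 0.148. The age difference in change is (0.75 - 0.60) - (0.88 - 0.83) = 0.10. By the normal formula, n = 2 x (1.960 + 1.282)^2 x 0.148^2 / 0.10^2, which gives 47 per group after rounding up. The t-test version gives 47.2, rounded up to 48. The section's wording leaves unclear whether 48 is per group or overall; the figures reproduce as per group.

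**5. Adding screen failure (assumed pass rates).** The 90% is illustrative. The other two are the shares of a normal distribution passing a single one-SD rule if volunteers score like the age norms: 84.13% if only low scores exclude, 68.27% if both tails exclude. Completers = 58 x pass rate x 0.80.

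| Assumed pass rate | Eligible of 58 | Completers per group | Screening needed for 60 enrolled |
|---|---|---|---|
| 90% | 52.2 | 41.8 | 60/0.90 = 66.7, so 67 |
| 84.13% | 48.8 | 39.0 | 60/0.8413 = 71.3, so 72 |
| 68.27% | 39.6 | 31.7 | 60/0.6827 = 87.9, so 88 |

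The chance of at least 48 completers from 58 screened is 0.7% in the second row and below 0.001% in the third.

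**6. Power at the reduced numbers** (normal approximation, inputs as in step 4): 48 per group, 91%; 46, 90%; 44, 89%; 39, 85%; 32, 77%. The dropout slip on its own therefore costs little power. The loss becomes material only when screen failures are added.

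**The case against.** A reader might set 58 beside 56 and infer that the plan allows exactly two screen failures per group. The documents do not say that 58 are screened to give 56 recruits. The figures stand in separate sections and each is tied directly to 48 completers. Given 48 x 1.2 = 57.6, the 58 is more plausibly an enrolment figure loosely called screening. That objection stands, but it leaves two inconsistent accrual figures, neither of which gives 48 at 20%.

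A reader might also infer that 116 cannot deliver the target because the criteria are bound to exclude many people. That rests on an assumption about scores. The stated purpose of the RBANS rule is to keep out early MCI or dementia, which favours reading it as a floor, and healthy volunteers may score above the norms. With a floor only, a shift of +0.5 SD removes about 3.9 of 58 and +0.8 SD about 2.1. Read as written, with both tails excluded, the same shifts remove more people: 21.8 and 26.5. The text does not say whether total or domain scores count. The remaining criteria can only add exclusions.

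Dropout is not defined. In Number of Subjects it could loosely cover all loss from screening onward: 58 to 48 is 17.2%, near enough to an approximate 20%. Sample Size Calculations, however, applies the rate to recruits. This is unresolved, and the plan should settle it.

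Finally, nothing caps or stops screening at 116. The form asks for an anticipated number, and accrual can be raised by amendment. So it cannot be said that the trial will finish short, only that its stated figures do not lead to its target.

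**Conclusion.** The point holds as a fault in the stated accrual figures. At the plan's own dropout rate, applied after enrolment, 58 gives 46.4 completers and 56 gives 44.8, against a target of 48. This needs no assumption about screening. No allowance for screen failure is stated, although a substantial set of criteria lies between screening and the challenge days.

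The size of any further shortfall depends on a pass rate that the documents do not give. Over the assumed range of 90% to 68%, 58 screened would yield about 42 to 32 completers. At 39 or 32 per group, power for the age-by-mecamylamine accuracy contrast would be about 85% or 77%. The stronger readings, that only two failures are allowed or that 116 is certain to fail, are not supported. The target of 48 is not in question.

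**What to change.** In Sample Size Calculations, Subject Selection and Number of Subjects:

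- Reconcile 58 with 56, and state screened, enrolled and completed counts separately, using the same figures in all three places.
- Set enrolment to 48 / (1 - 0.20) = 60 per group. If 56 is what is meant, restate the dropout rate as 14.3%.
- Say whether the 20% covers loss after enrolment only.
- Set the screening number to enrolment divided by an expected pass rate, and give its basis in the unit's earlier studies. For 60 enrolled, the table above gives 67, 72 or 88 per group.
- Add one sentence saying that screening continues until 48 per group have completed.

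The eligibility cut-offs, the completer target and the analysis stay as they are. The cost is a wording change, a larger accrual figure for the IRB and more screening visits.

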## INCLUSION OF WOMEN

The focus of this proposal is on cognitive changes in aging of the brain nicotinic systems. One half of the subjects will be women in this study. [name] has a proven track record of recruitment of women into studies such as the one proposed in this application as her research in the past has focused on cognition and menopause that occurs in older women. We also believe that the role of the nicotinic system in cognition does not differ by gender and thus we will recruit and equal number of men and women into the proposed study.

## INCLUSION OF MINORITIES

We are unaware of data to suggest differential performance on pharmacological challenge and cognition studies of racial/ethnic minorities when equated for cognitive level. Prior studies of the cognitive effects

of cholinergic agents have not found an ethnic/racial effect, but the studies have overwhelmingly been in Caucasians and most studies have not looked for such an effect. However, there is no a priori reason to suspect that the results from this study will not be generalizable to all populations. Our recruited patients for studies to date have been overwhelmingly majority, as reflects the very low presence of minority individuals in the areas that we recruit from (Northern New England, see Tables 2 & 3). Nonetheless, assisted by the CRC effort to recruit minority subjects for clinical research studies, we will be actively soliciting minority patients from area practitioners. In sum, while questions remain about ethnic/racial issues in studies of cholinergic and dopaminergic effects on cognition, we expect the results to be generalizable in spite of low minority participation. This study will make every attempt to recruit members of all racial/ethnic groups within the limits of our available population.

**Table 1. National Demographics for Normal Volunteer Populations (% of total population; male not reported)**

	American Indian or Alaskan Native %	Asian or Pacific Islander %	Black, not of Hispanic Origin %	Hispanic %	White, not of Hispanic Origin %	Other or Unknown %	Total %
Female	0.4	1.4	6.3	4.3	38.7	0	51

**Table 2. Local Racial Demographics for Normal Volunteer Populations (% of total population, based on 2000 Census)**

	American Indian or Alaskan Native %	Asian or Pacific Islander %	Black, not of Hispanic Origin %	White, not of Hispanic Origin %	2 or more Races %	Other or Unknown %	Total %
Vermont	0.4	0.9	0.5	96.8	1.2	0.2	100

**Table 3. Local Ethnic Demographics for Normal Volunteer Populations (% of total population, based on 2000 Census)**

	Caucasian %	Hispanic %	Total %
Vermont	99.1	0.9	100

**Outreach Program for Increasing Minority Participation:** We are able to draw on the CRC Minority Outreach Program to try to increase minority participation in our research studies. The CRC assisted information dissemination is an outreach to the small minority communities that do exist in our region. A description of this program is as follows:

The State of Vermont has a population of 606,000 people and 98% of them are Caucasian. Despite two programs to relocate Vietnamese and Laotian refugees in the State of Vermont, the number of minorities, both in absolute numbers and as a percentage of the total population, remains unusually low.

In some studies, certain investigators have achieved adequate numbers of minorities in their studies. Achieving this goal, however, has remained problematic and elusive for most other investigators. These efforts are further hampered by the increasing suspicion amongst some minority constituents that the research community is sometimes more interested in filling a quota than in contributing to their present and future well-being. This problem is obviously compounded by the extremely low percentages and absolute numbers of individuals of a given minority, which can often result in the same individual being repetitively polled to participate in the studies of different investigators.

The Administrative Manager of the CRC has held a series of meetings and discussions to try and develop a workable policy to address the issues of minority recruitment. Input was solicited from the

following individuals or organizations:

The National Institute of Health Guidelines on Inclusion of Women and Minorities  
The University of Vermont Commission on Racial Equality and Multicultural Education  
The Office of Minority Health, The Vermont State Department of Health  
The African/Latino/Asian/Native American Health Summit Report from Burlington, Vermont (ALANA)  
The Office of Research on Minority Health of the National Institutes of Health  
The Vice-Provost for Research of the University of Vermont  
Dean of the College of Medicine of the University of Vermont  
Vermont Senators, The Honorable [name] and The Honorable [name]  
Vermont Congressman The Honorable [name]  
American Indian Law Center, Albuquerque, New Mexico  
The Director of Office for the Protection of Research Risks (OPRR)  
CRC Scientific Advisory Committee

These discussions resulted in the formulation and acceptance of formal CRC goals and guidelines for minority research. The guiding principle accepted from that document was that "As the CRC becomes involved in studies investigating questions about health and disease issues in communities as well as individuals, the implications for the communities involved in studies need to be taken into account. Perspectives gained from members of the community during the conception and design of any research will enhance understanding of the focus of the research, encourage community participation and ensure that cultural, religious, spiritual and community values will not be undermined or ignored during the study."

The CRC Outreach Program is, consequently, focused primarily on the dissemination of information about opportunities for participation in clinical research. Once approved by the IRB and CRC Scientific Advisory Committee, this protocol will be eligible to be processed through the Outreach Program. The components of this program are as follows:

1. Incorporation of a brief description of the study, the study population, and the contact person and telephone number into a news sheet produced from CRC administration and entitled Study Highlights. This news sheet is not only posted prominently throughout the University of Vermont Medical Center and the University of Vermont campus, but is made available to publicity officers both within and outside the institution.
2. Dissemination of individual announcements, or the Study Highlights document described above, through newspaper or radio or television announcements. Although individual investigators are often required to pay for these services, the Program has been successful in many cases in reducing or entirely abolishing the normal fees associated with such advertising processes.
3. Dissemination of individual information or the Study Highlights document to the Office of Minority Health at the Vermont State Department of Health. [name], MSW, coordinates this office which has formed extensive ties to many community-based and professional organizations serving communities of color and minorities in Vermont. These organizations include Abenaki Self Help, ALANA Community Organization, Austin School for the Deaf, Burlington Community Health Center, Burlington Council on Refugees and Immigrants, Downland Native American Center, Vermont Refugee Assistance Program, Refugee Resettlement Program, Tibetan Resettlement Project, Vietnamese Association, Vermont Red Cross Language Bank, Africans in Motion for Communities of Color, Vermont Human Rights Commission, Burlington Community Economic Development Office, Green Mountain Lao Association, Missisquoi Health Center, Vermont Coalition for Lesbian and Gay Rights, Vermont Aids Council, American Civil Liberties Union, Racial Justice and Equity Project, Multicultural Council of Vermont, Medical Student Alana Group and Community Health Awareness Project. Many of these organizations have either informal, or increasingly, formal information networks often including newsletters. The Office of Minority Health also keeps an up-to- date listing of interpreters who are available throughout the State of Vermont to translate consent forms and dialogues between investigators and subjects into any of the numerous languages and dialects spoken amongst these communities.

**Inclusion of Children:** Describe efforts to include children. Inclusion is required unless a clear and compelling rationale shows that inclusion is inappropriate with respect to the health of the subjects or that inclusion is inappropriate for the purpose of the study. If children are included, the description of the plan should include a rationale for selecting or excluding a specific age range of children. When included, the plan must also describe the expertise of the investigative team in working with children, the appropriateness of the available facilities to accommodate children, and the inclusion of a sufficient number of children to contribute to a meaningful analysis relative to the purpose of the study. **If children are excluded** then provide appropriate justification. Provide target accrual for this population.

